ICH	International Conference on Harmonisation
IEC	Independent Ethics Committee
IHC	Immunohistochemistry
irAEI	immune-related adverse events of interest
IRB	Institutional review board
IB	Investigator's Brochure
ICF	Informed Consent Form
IgG4	Immunoglobulin G4
LLN	Lower limit of normal
mAb	Monoclonal antibody
MMR	Mismatch repair system
dMMR	Mismatch repair deficient
pMMR	Mismatch repair proficient

Dostarlimab
 GEICO 120-R & 120-T (DORA Study)

Abbreviation	Definition
MSI	Microsatellite instability
MSI-H	High microsatellite instability
MSI-L	Low microsatellite instability
MSS	Microsatellite stable
NCI	National Cancer Institute
NIH	National Institutes of Health
NGS	Next generation sequencing
NSMP	non-specific molecular profile
ORR	Objective response rate
OS	Overall survival
PCR	Polymerase chain reaction
PD1	Programmed cell death-1
PD-L1/2	Programmed death-ligand ½
PFS	Progression-free survival
PK	Pharmacokinetics
PIS	Patient Information Sheet
POLE	DNA polymerase epsilon
PR	Partial response
PRO	Patient reported outcomes
PS	Performance status
RECIST	Response Evaluation Criteria in Solid Tumors
SAE	Serious adverse event
SOC	Standard of care
SUSAR	Suspected unexpected serious adverse reaction
TCGA	The Cancer Genome Atlas
TEAE	Treatment-emergent adverse events
ULN	Upper limit of normal

1. SUMMARY

1.1. Study Design

1.1.1. Primary Clinical Objective

- To assess the antitumor activity of dostarlimab in patients with recurrent or advanced mismatch repair deficient (dMMR)/microsatellite instability-high (MSI-H) endometrial cancer, in terms of objective response rate (ORR) and duration of response (DOR) based on investigators' assessment using Response Evaluation Criteria in Solid Tumors (RECIST) v1.1.

1.1.2. Secondary Clinical Objectives

- To assess the effectiveness of dostarlimab in terms of investigator-assessed progression-free survival (PFS) and overall survival (OS).
- To analyze the PFS rate at 6, 12, 18 and 24 months.
- To assess the disease control rate (DCR) based on investigators' assessment using RECIST 1.1.
- To evaluate duration of treatment with dostarlimab.
- To describe the time to response to dostarlimab.
- To evaluate the safety and tolerability of dostarlimab in patients with dMMR/MSI-H endometrial advanced cancer, including immune-related adverse events of interest (irAEI).
- To evaluate Neutrophil-to-lymphocyte ratio as a potential predictive biomarker for treatment with dostarlimab.

1.1.3. Translational Objectives

- To compare centralized immunohistochemistry (IHC) re-testing with local testing.
- To compare centralized IHC re-testing results with two PCR-based techniques (Promega® and Idylla®) and with possible MMR gene alterations (genetic and epigenetic).
- To analyze the overall response rate and progression-free survival of the dMMR/MSI population selected by each biomarker technique: IHC, Polymerase chain reaction (PCR) Promega®, PCR Idylla®, or gene alteration (next generation sequencing (NGS)/hypermethylation).

1.1.4. Population

The study population consists of adult female patients with diagnosis of dMMR/MSI-H recurrent or advanced endometrial cancer with progression to a previous platinum regimen, who were treated within the Spanish dostarlimab Expanded Access Program (EAP).

1.1.5. Treatment Under Observation

In this study, the treatment under observation is dostarlimab administered on day 1 of each treatment cycle until disease progression, unacceptable toxicity or patient/doctor’s decision. The recommended dose for dostarlimab is 4 cycles of 500 mg every 3 weeks followed by 1000 mg every 6 weeks for all subsequent cycles.

1.1.6. Operational Milestones

Table 2: Table of Study Milestones

Number of Patients	Around 100-110
Enrollment Rate (patients/month)	Around 35
Number of Sites	50-60
Country	Spain
Study Duration	3 months (recruitment)
FPI (date)	December 2022
LPLV (date)	March 2023
Publications and/or Other Reports	September 2023 (Clinical Study) September 2024 (Translational Study)

2. BACKGROUND AND SIGNIFICANCE

2.1. Introduction to endometrial cancer

In Europe, endometrial cancer (EC) is the most common gynecological tumor and the fourth among cancer in women (1). There has been an increase in recent years in the incidence of EC, likely associated with the aging of the population and the increase in obesity. The incidence of EC may continue growing in the following decades (2). In 2018, an estimated 382,069 new cases and 89,929 deaths were attributed to this cancer type worldwide (3). Mortality from EC has not been modified in recent years, in large part driven by high grade carcinomas that are more likely to present at an advanced stage and to ultimately recur.

EC are classified into various histological subtypes, which differ in frequency, clinical presentation, prognosis and associated risk factors. Most ECs are adenocarcinomas, and the most common of these is the endometrioid subtype (75% to 80% of diagnosed cases). The majority of patients are diagnosed with early-stage disease (Stage I or II) and have favorable outcomes (5-year overall survival of approximately 75-90%), whereas advanced stages and non-endometrioid histologies, such as serous, clear cell, undifferentiated and carcinosarcoma, in any stage, are known to be associated with a worse prognosis.

2.2. Metastatic endometrial cancer treatment

For distant dissemination of EC that is not susceptible to radical treatment, systemic therapy should be considered. However, patients who recur or present with more advanced disease have a low probability of response rates to conventional treatment and clinical outcomes are poor.

For most patients with metastatic EC chemotherapy will be the preferred treatment, with the combination of carboplatin and paclitaxel as the standard first-line regimen. The phase III GOG 209 trial demonstrated that this regimen was not inferior to the TAP scheme (paclitaxel, adriamycin, and cisplatin) in terms of efficacy and had a more favorable toxicity profile. The median PFS and overall survival (OS) with carboplatin and paclitaxel were 13 and 37 months, respectively (4). There have not been randomized clinical trials comparing chemotherapy with hormone therapy as first-line treatments.

There is no chemotherapy regimen approved in second line. Only limited data are available for some drugs derived from small single-arm studies, showing a poor clinical activity, with objective response rates (ORRs) of approximately 7% to 14%, and median overall survival (OS) of 6 to 11 month. Even for the agents with a higher ORR (13.5%), the reported median OS remained at <1 year (Table 1) (5).

Table 1. Summary of efficacy data of different drugs assessed after prior platinum-containing regimen in endometrial cancer

Agent	Endpoint	Summary of Results	Reference
Liposomal doxorubicin	ORR	N=45 ORR=9.5% Median DOR=2.7 months Median OS=9.2 months	GOG 129-H
Oxaliplatin	ORR	N=52 ORR=13.5% Median DOR=10 months (range: 4.1 to 50.3 months)	GOG 129-K
Docetaxel	ORR	N=26 ORR=7.7% Median OS=6.4 months	GOG 129-N
Topotecan	ORR	N=28 ORR=9% Median DOR=4.5 months (N=2 responses) Median OS=N/A	GOG 129-J
Bevacizumab	ORR	N=52 ORR=13.5% Median DOR=6 months Median OS=10.6 months	GOG 229-E

DOR=duration of response; N=number of patients; N/A=not applicable; NR=not reached; ORR=objective response rate; OS=overall survival. Of note: none of these therapies are approved for treatment of endometrial cancer.

In addition to chemotherapy, some patients with EC may benefit from hormone therapy, mainly those with low-grade tumors and positive hormone receptors. Various hormonal drugs (progestins, selective estrogen receptor modulators, gonadotropin-releasing hormone analogs, and aromatase inhibitors) have been evaluated in phase II and retrospective studies, demonstrating modest activity, with a highly variable ORR (5%–56%) and short PFS (median 2–9 months) (6,7). A recent randomized phase II trial showed that the ORR and PFS associated with letrozole were significantly increased with the addition of palbociclib (8). Hormone therapy can be used in the second- line setting, but also in highly selected patients in the first-

line setting (those with low-grade EC with positive hormone receptors, low tumor burden, and slow growth).

2.3. Mismatch repair deficient (dMMR)/microsatellite instability-high (MSI-H) endometrial cancer

EC classification has changed from the Tumor Cancer Genome Atlas (TCGA) and ProMisE studies, resulting in a molecular classification with prognosis and therapeutic implications (9,10). Four subtypes were defined with the following molecular features: mutations in *DNA polymerase epsilon* (POLE), (representing 9-10% of total); MMRd (20-30%); p53 wild-type or non-specific molecular profile (NSMP) (43-50%); and p53 abnormal (12-27%).

dMMR defects can occur somatically or germline due to mutations or hypermethylation of their promoters. There are two commonly accepted approaches for the identification of dMMR. The first one is based on the expression of MLH1, PMS2, MSH2 and MSH6 proteins by IHC. Conserved expression or loss of one or more proteins classify patients in MMR proficient (pMMR) and dMMR. The other approach is based on PCR amplification of repetitive regions known as microsatellites within the genome. Amplified microsatellite loci by PCR establish high microsatellite instability (MSI-H) when two or more markers show instability, low MSI (MSI-L) when only one marker is altered, or stable, when none of the markers show instability (microsatellite stable, MSS). Different microsatellite panels have been developed. Promega® 1.2 is a commercial kit based in the Bethesda panel (5 markers commonly studied), but there are other commercially available based on the expression of different markers, as the Idylla® MSI system analyzed the expression of 7 markers. There are other approaches based on discrete panel by PCR, but also commercial solutions based on NGS.

Tumors with dMMR/MSI-H are associated to a high tumor mutational load, to a large number of neoantigens and to tumor-infiltrating lymphocytes, characteristics that confer a higher probability to respond to immune checkpoint inhibitors.

In the last 5 years, immunotherapy is undergoing an important development in EC. The first evidence of clinical activity of an immunotherapy in EC was obtained in a phase II trial published in 2015. The efficacy of the anti-programmed cell death 1 (anti-PD-1) monoclonal antibody pembrolizumab was studied in three cohorts of patients with metastatic solid tumors: dMMR colorectal cancer, pMMR colorectal cancer, and dMMR non-colorectal cancer. The ORR and progression-free survival (PFS) at 20 weeks for the dMMR non-colorectal cancer cohort (which included 2 EC patients) was 71% and 67%, respectively (11). These results confirmed the role of MMR status as a predictive biomarker to immunotherapy, and pembrolizumab was the first treatment approved by United States Food and Drug Administration (FDA) for dMMR tumors that had progressed to a previous line of treatment, regardless of the type of neoplasm. Other anti-PD-1 and anti-PD-L1 antibodies, like avelumab

or durvalumab, have achieved ORR ranging from 27% to 58% in highly pretreated patients with dMMR EC (12,13).

2.4. Background of Dostarlimab

2.4.1. Mechanism of Action and Development

Dostarlimab (formerly referred to as TSR-042) is a humanized immunoglobulin G4 (IgG4) monoclonal antibody (mAb) that binds with high affinity and specificity to the immune checkpoint receptor, programmed cell death-1 (PD-1). PD-1 is expressed on the surface of activated T-cells, forming part of a complex system of receptors and ligands that are involved in controlling T-cell activation. Binding of PD-1 to its ligands (PD-L1, PD-L2) reduces T-cell activity in the peripheral tissues during an inflammatory response, limiting lytic ability (14,15). PD-L1 and PD-L2 are commonly upregulated on many tumor types in response to multiple proinflammatory molecules. Their binding to PD-1 on T-cells contributes to T-cell exhaustion, protecting tumor cells from immunologic surveillance and promoting immune suppression; blockade of this pathway with a PD-1 inhibitor can therefore enhance anti-tumor effector function, resulting in decreased tumor growth (16,17).

Dostarlimab was generated using a proprietary platform that employs affinity maturation to select highly specific antibodies with desired functional characteristics. The functional antagonist activity of dostarlimab was confirmed in a mixed lymphocyte reaction assay, demonstrating enhanced Interleukin-2 (IL-2) production upon the addition of dostarlimab. Dostarlimab has an acceptable safety profile based on toxicology studies in monkeys and in nonclinical experiments. Based on published clinical experience with antibodies of the same drug class and the nonclinical data for dostarlimab, the safety and activity profile of dostarlimab is in line with the expectations for this class of agent.

2.4.2. Clinical Experience

The efficacy and safety of dostarlimab were investigated in GARNET (Study 4010-01-001), a multicenter, non-randomized, multiple parallel cohort, open label study conducted in patients with advanced solid tumors.

The recruitment began in March 2016 and the trial was conducted in 2 parts. Part 1 was a dose-escalation study to evaluate weight-based doses of dostarlimab. Part 2A evaluated the safety of non weight-based fixed doses of dostarlimab, while part 2B enrolled patients into several expansion cohorts based on tumor type and MMR status (regarding EC, cohort A1 included patients with dMMR tumors, and cohort A2 included patients with pMMR tumors) to assess the antitumor activity and safety of dostarlimab.

Part 1 employed a modified 3 + 3 design to evaluate ascending weight-based doses of intravenous infusion. Part 2A assessed the safety and tolerability of two fixed doses of

dostarlimab. No dose-limiting toxicities were observed, and the recommended therapeutic dose was determined to be 500 mg every 3 weeks for the first 4 cycles followed by 1000 mg every 6 weeks for all subsequent cycles, based on the efficacy, safety, receptor occupancy (fully occupied at all dose levels), and pharmacokinetics analysis. This dosing schedule was selected for part 2B.

In expansion A1 cohort of part 2B eligible patients had recurrent or advanced dMMR/MSI-H EC, with measurable disease that had progressed after a platinum-containing chemotherapy regimen (administered in the adjuvant setting or for the advanced disease) and were to have received no more than 2 lines of therapy for advanced or recurrent disease. The primary objective of the A1 cohort analysis was to evaluate the antitumor activity of dostarlimab by assessing the ORR by blinded independent central review (BICR) using RECIST v1.1, and DOR.

The secondary endpoints included the following: 1) DCR, defined as the proportion of patients with an objective response or stable disease lasting 12 weeks or longer, based on BICR using RECIST 1.1 criteria; 2) immune-related ORR (irORR) and immune-related DOR (irDOR) based on the investigator assessment using immune-related RECIST (irRECIST); 3) PFS, based on BICR using RECIST 1.1; 4) immune-related PFS, based on the investigator assessment using irRECIST; and 5) OS.

A total of 104 patients with MMRd EC were enrolled and treated with dostarlimab. The first interim efficacy analysis (data cut-off: July 2019) was performed on only 71 patients who had at least 1 measurable lesion and a minimum follow-up of 6 months. Baseline characteristics of these patients were: median age 64 years and Eastern Cooperative Oncology Group (ECOG) PS 0 (35%) or 1 (65%). A total of 65.3% were FIGO (International Federation of Gynecology and Obstetrics) Stage IV at the most recent assessment, and 69.7% had a histologic diagnosis of endometrioid carcinoma Type 1. The most common disease grade at diagnosis was Grade 2 (40.3%). Only half of the patients had received prior treatment for metastatic disease, and the median PFS from the last platinum regimen was 6.4 months (range, 1.6–79.6).

With a median follow-up of 11.2 months, 30 patients achieved an objective response (ORR 42.3%; 95% CI 30.6%–54.6%): 9 patients (12.7%) had a complete response, and 21 (29.6%) had a partial response. All patients with a confirmed complete response remained in response as of the data cutoff date. The ORR was observed independently of histologic subtype and previous lines of therapy, although the subgroup analyses were not powered and should be interpreted with caution. Although the median DOR was not reached, it was estimated that 96.4% of the patients would have a sustained response at 6 months and 76.8% at 12 months. The DCR was 57.7% (95% CI 45.4%–69.4%), and the median PFS was 8.1 months (95% CI 3.0–18.0). The median OS was also not reached, with an estimated 76.9% of patients alive at 12 months (18).

The second interim analysis (data cut off: March 2020), with a median follow-up of 16.3 months, was performed on 103 patients, showing an ORR of 44.7% (95% CI 34.9%–54.8%) and a DCR of 57.3% (95% CI 47.2%–67%). 89.1% of patients had a response ongoing, and the median DOR was not reached yet. The estimated probabilities of remaining in response at 6, 12 and 18 months were 97.8%, 90.6%, and 79.2%, respectively (19).

A subanalysis by the number of prior lines of this cohort has been presented. Patients with only 1 prior line (n = 66) achieved an ORR of 50% (95% CI 37.4–62.6), while patients with 2 or more prior lines (n = 39) achieved an ORR of 35.9% (95% CI 21.2–52.8). 70% of the patients with 1 prior line and 67% of the patients with 2 or more prior lines remained in response at the data cutoff date (19).

At 2022 American Society of Clinical Oncology (ASCO) meeting the latest update from the third prespecified interim analysis was presented (Data cutoff date: November 1, 2021). A total of 151 patients (143 in the efficacy-evaluable population) with dMMR EC were enrolled and treated with dostarlimab in A1 cohort.

With a median follow-up of 27.6 months, 45.5% of patients achieved an objective response (95% CI 37.1%– 54.0%): 16.1% had a complete response and 29.4% had a partial response. 83.1% had an ongoing response at the data cut-off. Although the median DOR was not reached, it was estimated that 96.8% of the patients would have a sustained response at 6 months, 93.3% at 12 months and 83.7% at 24 months. The DCR was 60.1% (95% CI 51.6%–68.2%) and the median PFS was 6.0 months (95% CI 4.1–18.0). The estimated PFS was 46.4% at 12 months and 40.1% at 24 months. The median OS was also not reached, with an estimated 73.3% of patients alive at 12 months and 60.5% at 24 months (20).

Description of selected adverse reactions

Of the 104 patients included in the safety analysis of the A1 cohort, 65.4% had a treatment-related adverse event (TRAE), most of which were mild (grade 1 or 2). The most frequent TRAEs were asthenia, diarrhea, fatigue, and nausea. The incidence of grade 3–4 TRAEs was 11.5%; 10 patients (9.6%) experienced at least 1 grade 3–4 TRAE, with colitis the most frequent event (2 [1.9%]). Only two patients (1.9%) had to discontinue the study because of a TRAE (transaminase increase). Immune-related TRAEs were reported in 23.1% of the patients, with diarrhea (5.8%) and hypothyroidism (5.8%) the most frequent; only 6.7% of these TRAEs were grade 3–4. No deaths due to treatment-related AEs were reported (18).

Data on patient-reported outcomes were available for 66 of the 104 patients who were administered 1 or more doses of dostarlimab. These outcomes showed that dostarlimab was, generally, well tolerated, and key disease-related symptoms, such as pain and fatigue, improved while on the treatment. Several AEs, such as nausea, vomiting, constipation, and diarrhea, remained relatively stable compared with baseline over the course of the treatment.

Dostarlimab
GEICO 120-R & 120-T (DORA Study)

At the latest interim analysis presented at ASCO 2022 meeting, 17.6% of patients had TRAE grade 3 or higher and in 8.5% led to discontinue the treatment.

The toxicity reported for cohort F of the GARNET trial was similar to the dMMR EC cohort. 68.8% of the patients experienced a TRAE, and 8.3% experienced at least 1 grade 3 or higher TRAE. Only two patients (1.8%) discontinued dostarlimab due to a TRAE, and no deaths were attributed to the drug (21).

3. STUDY RATIONALE

There is a paucity of real-world data of patients with EC treated with dostarlimab, something that has an especial interest considering the limited evidence available with dostarlimab (only a phase I open-label study).

Moreover, there are only some discrete published studies comparing different dMMR/MSI-H approaches in EC and there are almost not data assessing their correlation to ORR of immunotherapy. To our knowledge only one phase II trial with avelumab made a comparison of dMMR/MSI-H tested by IHC, PCR or NGS, but only 15 patients were assessed in the dMMR cohort.

In January 2021, GlaxoSmithKline opened an EAP in Spain to make dostarlimab available to eligible women with recurrent or advanced dMMR/MSI-H endometrial cancer, a clear unmet medical need for these endometrial cancer patients.

EAPs allow patients with a serious or life-threatening disease or condition who are not otherwise eligible to participate in a clinical trial and have no other comparable or satisfactory therapeutic options to access drugs, with demonstrated benefit in clinical trials, that are pending approval.

This study seeks to evaluate the efficacy and tolerability of dostarlimab in recurrent or advanced dMMR/MSI-H endometrial cancer patients treated in a real world setting within the Spanish EAP. In addition, the translational study aims to assess the efficacy according to the biomarker technique used (IHC, PCR Promega®, PCR Idylla®, or gene alteration by NGS/hypermethylation).

4. STUDY DESIGN

4.1. Overview

This is a multicenter, retrospective, observational (non-interventional) study, in patients treated in a real-world setting within the Spanish dostarlimab EAP. The study is planned to be conducted in the Medical Oncology departments at 50-60 Spanish GEICO-associated hospitals. Its multicenter nature aims to improve the representativeness of the study population in Spain. The study would include approximately 110 patients with dMMR/MSI-H recurrent or advanced EC, that have progressed on or following prior treatment with a platinum-containing regimen, treated within the dostarlimab EAP, available in Spain from January 2021 to September 2022. The total number of participating centers and patients will be confirmed once the EAP is closed.

Patient's medical records will be screened by local clinical staff to assess for eligibility according to selection criteria. The study comprises a single study visit, in which the patient will give her informed consent to participate (when the patient is alive) and the physician will extract the study data from the patient's medical charts.

Alive patients who fulfill inclusion criteria and meet no exclusion criteria will be informed by a member of their care team about the purpose of the study, as well as about potential risks and benefits of study participation. The written informed consent form (ICF) should be signed prior to study initiation in alive patients in order to access their medical records. Deceased patients will be still included but their relatives will not be contacted. In these instances, data will be collected by members of the direct care team, unless there is a prior express order from the patient to preserve confidentiality. All eligible deceased and consenting living patients at the participating centers will be included. Data will be directly retrieved from hospital medical records and reported in the electronic Case Report Form (eCRF).

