7. STANDARD OF CARE

In this retrospective observational study, patients will not be exposed to clinical interventions different from those belonging to the standard of care. There are no study-specific procedures other than the normal activities that patients would undergo if they were not participating in the study. Accessible/reachable patients will be interviewed during routine care visits and principal investigators at each site will offer them the possibility of participating in the study. This will involve reading and signing the ICF.

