8. DATA COLLECTION PROCESS

8.1. Patient Information and Consent

All patients participating in the study (accessible, alive patients who can be interviewed in the hospital) will receive a Patient Information Sheet (PIS) describing, in simple language, the goals, scope, procedures and relevant implications of the study. The PIS will integrate an ICF to be signed by the patient, which is indispensable for study participation (for accessible patients). Written informed consent must be given by each accessible/reachable patient before study initiation (prior to registration of the patient in the eCRF). The PIS/ICF will include the consent of patients for the collection and analysis of their clinical data.

Data of inaccessible/unreachable patients (dead, lost, etc.) could still be used according to the permissions of ethics committees and Spanish law, regarding the use of data in retrospective studies.

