8.3. Data Sources

Considering the retrospective nature of this study, the source of information will be the patient's medical chart. Other potential sources of data are pharmacy records, databases or electronic prescribing systems. The data to be extracted in this study which are available in the patient's medical charts will be recorded in the eCRFs. Only data obtained before study initiation (the date of the first ethics committee approval) will be extracted from the patient's medical chart in order to ensure they are retrospective in nature. Data unavailable in patients' medical charts will be mentioned in the eCRFs as "not available". The degree of detail and completeness of data extracted for this study will depend on their availability according to local clinical practice. The investigator participating in this study will revise patient's medical chart to confirm eligibility of the patient. Once it is confirmed that all selection criteria are met and informed consent is given, the investigator will proceed to extract the study data available

(previously registered) in patient's medical charts and completing the eCRF. Patient medical information obtained by this study is confidential and may only be disclosed to third parties as permitted by the informed consent form signed by the subject, unless permitted or required by law. Confidentiality standards will be maintained by coding each patient enrolled in this study through assignment of a unique subject identification number.

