9. STATISTICAL ANALYSIS

Statistical analyses and study reports will be developed by the Coordinating Investigator of the study in collaboration with the biostatisticians of the study Contract Research Organization (CRO). The World Programming System (WPS) platform (a SAS language software) will be used for these analyses.

All variables will be summarized separately. Depending on the type of the variable, the following statistics will be reported:

- Continuous variables: number of subjects (n), number of missings, mean, standard deviation (STD), median, standard error (SE, if needed), 25th and 75th percentiles, minimum, and maximum.
- Categorical variables: frequencies and percentages (calculated over the number of non-missing values).

In general, minimum and maximum are going to be reported using the same number of decimal places as collected in the raw data. Mean, STD, median, 25th and 75th percentiles will be reported with one additional decimal place.

Time to event data will be listed and summarized at every specified timepoint using the number patients at risk, number of patients censored, number of patients with the event, Kaplan Meier estimate (%), and the 95% confidence interval. In addition, 25th, 50% and 75th percentiles from Kaplan-Meier curves will be used.

Progression-free survival is defined as the time from the date of the first administration of dostarlimab and the occurrence of disease progression or death, whichever occurs earlier.

Overall survival is defined as the time between the start of treatment and death. Patients alive at the last follow-up will be censored for the analysis of OS.

Both PFS and OS will be analyzed using the Kaplan-Meier method. The responses (valid only for patients who have started dostarlimab with measurable disease) will be assessed following the RECIST 1.1 criteria and reported in percentages.

Further details on statistical analyses will be specified in the Statistical Analysis Plan (SAP).

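### Deceased patients enter without consent but living patients only with it, so Kaplan-Meier OS is biased downward to the extent that known-living patients are missed more often than the deceased; sections 4.1, 8.1 and 8.3 also disagree on lost patients

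*Protocol*

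**What the plan says.** **Entry rule.** Protocol section 4.1 closes its description of recruitment with "All eligible deceased and consenting living patients at the participating centers will be included". Relatives of deceased patients are not contacted, and the records of the deceased are used "unless there is a prior express order from the patient to preserve confidentiality". Living patients must sign before their records are opened.

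**How consent is sought.** Section 7: "Accessible/reachable patients will be interviewed during routine care visits". Section 8.1 makes the signed form a condition of participation for accessible patients.

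**Lost patients.** Section 8.1 adds: "Data of inaccessible/unreachable patients (dead, lost, etc.) could still be used according to the permissions of ethics committees and Spanish law". Section 4.1 has no such category. Section 8.3 lets data extraction start "Once it is confirmed that all selection criteria are met and informed consent is given" and states no exception.

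**Analysis.** OS is a secondary objective (4.2.2). Section 9 measures it from start of treatment to death, by Kaplan-Meier, and states: "Patients alive at the last follow-up will be censored for the analysis of OS".

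**Limitations.** Section 8.4 names incomplete documentation, missing data and under-recorded adverse events. It does not name selection by vital status.

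**The concern.** Whether a patient's data enter the study depends on whether she has died, and death is the OS event. A living patient who refuses is removed from every risk set she would have belonged to. A deceased patient with the same start date stays in and contributes her event. The hazard is then computed over too small a denominator, and the curve sits too low. A larger sample does not cure this, and the confidence interval does not show it.

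The second problem is the text on lost patients. Section 8.1 would permit their inclusion, 4.1 leaves them out, and 8.3 read literally requires consent from everyone. With 50-60 sites, one centre could include a lost patient whom another leaves out.

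At stake is how far the OS curve describes all patients treated in the expanded access program at the participating centers. Without a count of those not included, a reader cannot tell a negligible shift from a material one.

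**Working it through.** The protocol states no OS figure, event count or capture rate of its own, so there is nothing to reproduce. The check asks for the direction of the effect, and then its size under stated assumptions.

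**Inputs**
- OS shape, from the earlier trial of the drug (section 2.4.2): "an estimated 73.3% of patients alive at 12 months and 60.5% at 24 months".
- Treatment starts from January 2021 to September 2022, 21 months (section 4.1). Uniform entry is assumed.
- 110 patients treated (sections 4.1 and 6).
- Data cut-off at month 23, 25 or 27 after the start of January 2021. Section 8.3 limits data to before the first ethics approval, whose date is not given. First patient in is December 2022 (section 1.1.6), so the earliest value is the most plausible.
- Assumed: a share c of living and d of deceased patients is captured, at random within each group.

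**Survival model (piecewise exponential)**
- Months 0-12: h = -ln(0.733)/12 = 0.0259 per month.
- Months 12-24: h = -ln(0.605/0.733)/12 = 0.0160 per month.
- True 18-month OS: 0.733 x exp(-6 x 0.0160) = 66.6%.
- Share alive at cut-off: 75, 72 or 69% for month 23, 25 or 27. At 72%, about 79 of 110 are alive, so missing 5, 10, 20 or 30% of them is about 4, 8, 16 or 24 patients.

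**Hazard that Kaplan-Meier sees**

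h*(t) = h(t) x d / [d(1 - a) + c x a]

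Here a is the share of those at risk at time t who are still alive at the cut-off: the mean of S(follow-up)/S(t) over patients whose potential follow-up reaches t. If c = d, the factor is 1 and there is no bias. If c < d, it exceeds 1 and OS falls. Example at t = 0, cut-off month 25, c = 0.80, d = 1: 1/(0.28 + 0.80 x 0.72) = 1/0.856 = 1.17, a hazard 17% too high.

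**Results, integrating h*(t); ranges are over the three cut-offs**

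| Living captured | Deceased captured | 12-month OS (true 73.3%) | 18-month OS (true 66.6%) |
|---|---|---|---|
| 95% | 100% | 72.3-72.4 | 65.4 |
| 90% | 100% | 71.3-71.4 (71.25-71.35 unrounded) | 64.1-64.2 |
| 80% | 100% | 68.9-69.1 | 61.2-61.5 |
| 70% | 100% | 66.1-66.5 | 57.8-58.2 |
| 90% | 95% | 72.3 | 65.3-65.4 |
| 80% | 80% | 73.3 | 66.6 |

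The 12-month falls with all deceased kept are about 1, 2, 4.3 and 7 points. The fifth row shows that leaving out 5% of the deceased, for instance through confidentiality orders, halves the fall at 90% capture to about 1 point. The last row confirms that the asymmetry causes the bias, not missing patients as such. A separate simulation with a Weibull as well as the piecewise shape gave the same picture.

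**Scale.** The 95% half-width at 12 months, n = 110, ignoring censoring, is 1.96 x sqrt(0.733 x 0.267/110) = 8.3 points. With the modelled censoring it is about 9.0.

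**The case against.** **No documented size.** The protocol gives no refusal or loss rate. Living patients are approached by their own care team, and section 6 expects most program patients to be analysed. The 4-7 point falls need 20-30% of the living to be missed, and nothing in the protocol supports such a rate. This stands: the direction for known-living patients follows from the entry rule, but the size does not.

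**Lost is not the same as living.** A reader might infer that every lost patient adds to the downward bias. The protocol does not support this. A lost patient's vital status may be unknown, and leaving out an unrecorded death pushes OS upward. This stands, and the conclusion is limited to patients known to be alive.

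**Section 8.1 already covers the lost, and 8.3 cannot be meant literally,** since it would bar the deceased whom 4.1 admits. This stands in part. The intention can be guessed, but 8.1 is permissive and conditional, and 4.1 still names only two groups. It also does nothing for accessible patients who refuse.

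**Some of this belongs elsewhere.** A sensitivity analysis can sit in the SAP and a screening log outside the protocol. Neither is shown, so their absence is not counted as a fault. The entry rule and the stated limitations are protocol matters.

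**Modelling.** Cut-offs at months 25 and 27 are later than the milestones suggest, and entry depends on vital status at the study visit rather than at cut-off. Both effects are small: the cut-off moves 12-month OS by at most about 0.4 points in the table, and a lag of 3-5 months softens the fall at 80% capture by about 0.1-0.4 points.

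**Conclusion.** The point holds in conditional form. Following section 4.1 as written makes entry depend on the OS outcome, and Kaplan-Meier OS is biased downward to the extent that known-living patients are missed at a higher rate than the deceased. For patients of unknown vital status the direction is open, and 4.1, 8.1 and 8.3 must be reconciled.

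The illustrative 12-month falls of about 1, 2, 4.3 and 7 points rest on the earlier trial's OS, uniform entry, complete capture of the deceased and random loss among the living. With 10% or fewer of the living missed, the shift is well below the 8.3-point half-width.

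A reader might infer that the study's OS will be materially understated, or that ORR, DOR and PFS are distorted too. The first needs a capture rate that the protocol does not give. The second was not computed and would need a link between response or progression and capture.

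Severity is minor to moderate: OS is a descriptive secondary outcome, with no test and no comparator.

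**What to change.** 1. **Reconcile the text.** Make 4.1 and 8.3 agree with 8.1: consent applies to accessible living patients, and unreachable patients are included where ethics committees and law permit, censored for OS at last known contact.
2. **Report totals.** Give the number of program-treated patients at participating centers who were not included, by last known vital status (alive, deceased, unknown) and reason (refused, lost, confidentiality order). Use study-level totals: at about two patients per site (110 over 50-60 sites), a per-site table would come close to individual data on people who refused.
3. **Add one OS sensitivity analysis,** in the SAP if preferred. Weight included living patients by known-living treated divided by known-living included. Take those of unknown status first as alive and then as deceased to give bounds. State the assumption that included patients represent those missed.
4. **Name selection by vital status** as a limitation in 8.4.

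**Cost.** Wording in three sections, a few counts and one analysis. Item 1 does not bring in patients who refuse; items 2 and 3 address them. The assumption behind the weight cannot be tested, and censoring lost patients at last contact may itself be informative. In 6,000 simulated cohorts of 110 treated (80% of the living captured, cut-off month 25), 1.96 SD of 12-month OS was 9.1 points weighted against 9.0 for the full cohort. The weight returns 73.3% when capture is unrelated to start date. If capture is 95% in one half of the start dates and 65% in the other, it leaves an error of up to about 1.4 points at 12 months and 2.7 at 18 months. It should not be used to correct ORR or PFS.
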